12.3. Disclosure of Information

Participants' medical information obtained as a result of this study is considered confidential, and disclosure to third parties other than those noted in this protocol is prohibited. Subject to any applicable authorization(s), all reports and communications relating to participants in this study will identify participants only by initials and number. Medical information resulting from a participant's participation in this study may be given to the participant's personal physician, other authorized parties, or appropriate medical personnel responsible for the participant's participation in this clinical study. Data generated in this study will be available for inspection on request by the FDA or other government regulatory agency auditors; the sponsor, the sponsor's medical monitor, and their designated representatives; the IRB/EC; and other authorized parties. All information concerning the study medication and the sponsor's operations (such as patent applications, formulas, manufacturing processes, basic scientific data, or other information supplied by the sponsor and not previously published) is considered to be confidential and shall remain the sole property of the sponsor. The investigator agrees to use this information only in conducting this study and not to use it for other purposes without the sponsor's prior written consent. The information developed in this clinical study will be used by the sponsor in the clinical development of voxelotor and, therefore, may be disclosed by the sponsor as required to authorized parties (including its corporate partners for the study drug, if any, and their designated representatives), other clinical investigators, pharmaceutical companies, the US FDA, and other government agencies. Any information, inventions, discoveries (whether patentable or not), innovations, suggestions, ideas, and reports made or developed by the investigator(s) as a result of conducting this study shall be promptly disclosed to the sponsor and shall be the sole property of the sponsor. The investigator agrees, upon the sponsor's request and at the sponsor's expense, to execute such documents and to take such other actions as the sponsor

deems necessary or appropriate to obtain patents in the sponsor's name covering any of the foregoing.

13. INSURANCE AND FINANCIAL DISCLOSURE

The sponsor has subscribed to an insurance policy covering, in its terms and provisions, its legal liability for injuries caused to participating persons and arising out of this research performed strictly in accordance with the scientific protocol, as well as with applicable law and professional standards.

Financial disclosure statements will be handled in a separate agreement apart from the protocol, kept on file, and submitted as applicable with any subsequent license application.

14. PUBLICATION POLICY

It is intended to publish the results of the study once all participants have completed the study and the study data have been analyzed.

The investigator or the sponsor may not submit for publication or present the results of this study without allowing each of the other parties to review and comment on the prepublication manuscript, as defined in the site's clinical trial agreement.

The investigator may not submit any of the results of the study for publication without the prior consent of the sponsor.

Appendix A. SCHEDULE OF ASSESSMENTS

Study Day/Week	Treatment Period								EOS
	First 48 Weeks					After Week 48			+7 days c
	Day 1 a	Week 12 b ± 5 days	Week 24 ± 10 days	Week 36 b ± 10 days	Week 48 ± 10 days	Q12Wk ± 10 days	Q24 Wk ± 10 days	Q48 Wk ± 10 days	
Informed Consent/Assent	X								
Review Inclusion/Exclusion Criteria	X								
Medical History	X								
Weight and Height d	X		X		X			X	
Abbreviated Physical Examination ^e	X				X				
Vital Signs ^f	X	X	X	X	X		X	X	X
Adverse Events	X	X	X	X	X		X	X	X
Concomitant Medications	X	X	X	X	X		X	X	X
Hematology ^g	X	X	X	X	X		X	X	X
Serum Chemistry h	X		X		X			X	X
Urine Pregnancy Test i	X	X	X	X	X		X	X	X
Taste and Palatability Questionnaire with InClinic Dosing ^j	Performed on Day of Switch, and at the following two consecutive visits								
Transcranial Doppler k	Performed as standard of care								
Study Drug Dispensing and Accountability ¹	X	X	X	X	X	X	X	X	X

Abbreviations: CRF, case report form; EOS, End of Study; Q12Wk, every 12 weeks; Q24 Wk, every 24 weeks; Q48 Wk, every 48 weeks; TCD, transcranial Doppler.

Study Day/Week	Treatment Period					EOS			
	First 48 Weeks			After Week 48			+7 days ^c		
	Day 1 ^a	Week 12 b ± 5 days	Week 24 ± 10 days	Week 36 b ± 10 days	Week 48 ± 10 days	Q12Wk ± 10 days	Q24 Wk ± 10 days	Q48 Wk ± 10 days	

Voxelotor

GBT440-038

- a. Day 1 assessments will be performed prior to dosing. If any of the Day 1 assessments were performed at the last study visit in the originating (parent) clinical study, and the Day 1 visit occurs on the same date, the tests do not need to be repeated.
- b. Week 12 and Week 36 planned visits for participants who roll over to this study from Study GBT440-042 will be for drug dispensing, collection of adverse events and concomitant medications only.
- c. The EOS visit should be conducted 4 weeks (28 days) after the last dose of study drug (+7-day window).
- d. Height and weight will be collected only for participants < 18 years of age.
- e. Will include general appearance; examination of eyes, skin, cardiovascular system, and respiratory system; abdominal examination; and a symptom-directed examination.
- f. Heart rate and blood pressure will be measured after participant has rested for ≥ 5 minutes in the seated or supine position. If the first vital sign measurement is outside the normal range and deemed clinically significant, the measurement will be repeated within 5 minutes.
- g. Will include the following: hematocrit, hemoglobin, mean corpuscular hemoglobin concentration, mean corpuscular volume, platelet count, red blood cell distribution width, reticulocytes (absolute and percent), and white blood cell count with differential.
- h. Will include the following: alanine aminotransferase, albumin, alkaline phosphatase, aspartate aminotransferase, bilirubin (total, direct, and indirect), blood urea nitrogen, creatinine, lactate dehydrogenase. Laboratory values for bicarbonate, calcium, chloride, glucose potassium, and sodium should only be recorded on the CRF if the laboratory value is abnormal and considered clinically significant by the Investigator).
- i. Will be performed for female participants of childbearing potential only. If the urine pregnancy test is positive, the result must be confirmed per local standard of care (eg, ultrasound or serum pregnancy test).
- j. Upon introduction of a new dosage form (either powder for oral suspension or dispersible tablets) or switch to higher dose (ie, modified dispersible tablet) to participants, a brief questionnaire will be administered to parents and/or children (aged ≥ 5 years) during the first visit when the transition is made and at the subsequent 2 scheduled visits.
- k. For all participants, results from TCD assessments performed as part of standard of care at each site will be recorded on the CRF.
- 1 Voxelotor will be dispensed in 12-week (~90-day) intervals with instruction to participants to return any used/unused bottles/stick packs to the clinic. At the Day 1 Visit, only study drug dispensing will be performed. At the EOS visit, only study drug accountability will be performed.

APPENDIX B. SCHEDULE OF ASSESSMENTS FOR SELECT SITES PARTICIPATING IN VOXELOTOR PLASMA AND WHOLE BLOOD PK COLLECTIONS UPON SWITCHING TO THE MODIFIED DOSE DISPERSIBLE TABLETS ^a

Study Day/Week	Day of Switch	14 Days Post-Switch	12 Weeks Post-Switch
PK Sample Collection (plasma and whole blood)	X	X	X
	(Predose)	(Predose)	(Predose)
Other Assessments	Per Scheduled Visit on Day of Switch (Appendix A) and must include Safety Assessments ^b Concomitant Medications Update	Safety Assessments ^b Concomitant Medications Update	Safety Assessments ^b Concomitant Medications Update
Taste and Palatability Questionnaire	X	X	X

Abbreviations: PK, pharmacokinetic.

Note: The last dose of voxelotor should be taken 24 hours (\pm 1 hour) before PK sampling. The participant or their caregiver are to record the time of the voxelotor dose taken prior to each of these visits.

CONFIDENTIAL 58

^a Once the modified dose DT is available, switching to the modified dose DT will begin for subjects starting this study after completion of their parent study. For subjects that are already enrolled on this study, switching will begin at the subject's next scheduled visit (eg, Week 12, Week 24, etc.).

^b Safety assessments include AE and SAE monitoring, protocol-specified hematology and serum chemistry tests, abbreviated PEs, and protocol-specified vital sign measurements.

Appendix C. LIVER SAFETY: SUGGESTED ACTIONS AND FOLLOW-UP ASSESSMENTS [AND STUDY DRUG RECHALLENGE GUIDELINES]

This appendix is included to support Study transition to Pfizer Pharmacovigilance processes and systems.

Potential Cases of Drug-Induced Liver Injury

Humans exposed to a drug who show no sign of liver injury (as determined by elevations in transaminases) are termed "tolerators," while those who show transient liver injury but adapt are termed "adaptors." In some participants, transaminase elevations are a harbinger of a more serious potential outcome. These participants fail to adapt and therefore are "susceptible" to progressive and serious liver injury, commonly referred to as DILI. Participants who experience a transaminase elevation above 3 × the upper limit of normal (ULN) should be monitored more frequently to determine if they are "adaptors" or are "susceptible."

Liver function tests (LFTs) are not required as a routine safety monitoring procedure in this study. However, should an investigator deem it necessary to assess LFTs because a participant presents with clinical signs/symptoms, such LFT results should be managed and followed as described below.

In the majority of DILI cases, elevations in AST (aspartate transaminase) and/or ALT (alanine transaminase) precede total bilirubin elevations (> 2 × ULN) by several days or weeks. The increase in total bilirubin typically occurs while AST/ALT is/are still elevated above 3 × ULN (ie, AST/ALT and total bilirubin values will be elevated within the same laboratory sample). In rare instances, by the time total bilirubin elevations are detected, AST/ALT values might have decreased. This occurrence is still regarded as a potential DILI. Therefore, abnormal elevations in either AST or ALT in addition to total bilirubin that meet the criteria outlined below are considered potential DILI (assessed per Hy's law criteria) cases and should always be considered important medical events, even before all other possible causes of liver injury have been excluded.

The threshold of laboratory abnormalities for a potential DILI case depends on the participant's individual baseline values and underlying conditions. Participants who present with the following laboratory abnormalities should be evaluated further as potential DILI (Hy's law) cases to definitively determine the etiology of the abnormal laboratory values:

- Participants with AST/ALT and total bilirubin values within the normal range who subsequently present with AST/ALT values $\geq 3 \times \text{ULN}$ AND a total bilirubin value $\geq 2 \times \text{ULN}$ with no evidence of hemolysis and an alkaline phosphatase value $\leq 2 \times \text{ULN}$ or not available.
- For participants with baseline AST **OR** ALT **OR** total bilirubin values above the ULN, the following threshold values are used in the definition mentioned above, as needed, depending on which values are above the ULN at baseline:
 - O Preexisting AST/ALT baseline values above the normal range: AST/ALT values ≥ 2 times the baseline values AND $\geq 3 \times \text{ULN}$; or $\geq 8 \times \text{ULN}$ (whichever is smaller).

O Preexisting values of total bilirubin above the normal range: total bilirubin level increased from baseline value by an amount of $\geq 1 \times ULN$ or if the value reaches $\geq 3 \times ULN$ (whichever is smaller).

Rises in AST/ALT and total bilirubin separated by more than a few weeks should be assessed individually based on clinical judgment; any case where uncertainty remains as to whether it represents a potential Hy's law case should be reviewed with the sponsor.

The participant should return to the investigator site and be evaluated as soon as possible, preferably within 48 hours from awareness of the abnormal results. This evaluation should include laboratory tests, detailed history, and physical assessment.

In addition to repeating measurements of AST and ALT and total bilirubin for suspected Hy's law cases, additional laboratory tests should include albumin, creatine kinase, direct and indirect bilirubin, gamma-glutamyl transferase, prothrombin time/international normalized ratio, eosinophils (%), and alkaline phosphatase. Consideration should also be given to drawing a separate tube of clotted blood and an anticoagulated tube of blood for further testing, as needed, for further contemporaneous analyses at the time of the recognized initial abnormalities to determine etiology. A detailed history, including relevant information, such as review of ethanol, acetaminophen/paracetamol (either by itself or as a coformulated product in prescription or over-the-counter medications), recreational drug, or supplement (herbal) use and consumption, family history, sexual history, travel history, history of contact with a jaundiced person, surgery, blood transfusion, history of liver or allergic disease, and potential occupational exposure to chemicals, should be collected. Further testing for acute hepatitis A, B, C, D, and E infection, total bile acids, liver imaging (eg, biliary tract), and collection of serum samples for acetaminophen/paracetamol drug and/or protein adduct levels may be warranted.

All cases demonstrated on repeat testing as meeting the laboratory criteria of AST/ALT and total bilirubin elevation defined above should be considered potential DILI (Hy's law) cases if no other reason for the LFT abnormalities has yet been found. Such potential DILI (Hy's law) cases are to be reported as SAEs, irrespective of availability of all the results of the investigations performed to determine etiology of the LFT abnormalities.

A potential DILI (Hy's law) case becomes a confirmed case only after all results of reasonable investigations have been received and have excluded an alternative etiology.

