1. INTRODUCTION

1.1. Disease Background

Sickle cell disease (SCD) is a rare, devastating, and debilitating disease marked by the pathophysiologic features of hemolytic anemia, vaso-occlusion, and progressive end-organ damage, with a clinical course characterized by life-long disability and early death. In addition to unpredictable and recurrent episodes of severe pain, commonly referred to as painful crises, a systemic vasculopathy leads to chronic and progressive tissue injury across multiple organ systems. Multiple pathophysiologic mechanisms likely contribute to the systemic vasculopathy, including, importantly, chronic hemolytic anemia (Rother, 2005).

The most devastating complication of pediatric SCD is the development of central nervous system (CNS) events. This may present as overt stroke or silent strokes, which are subclinical cerebral infarctions detected on brain magnetic resonance imaging. Almost 50% of the SCD population is pediatric (Farber, 1985), and approximately 11% of patients with SCD have clinically apparent strokes before the age of 20 years. The risk of stroke is highest during the first decade, and it is most significant between the ages of 2 and 5, when it reaches 1.02% per year. In addition to overt strokes, another 17% to 22% of children suffer silent strokes, which can produce significant neuropsychological deficits (Ohene-Frempong, 1998; Verduzco, 2009). The pathogenesis of stroke in children with SCD is complex and not fully resolved, but in most cases involves occlusion or stenosis of the large intracranial arteries. Histopathology varies, but in general the pattern is one of smooth muscle proliferation with overlying endothelial damage and fibrosis (Rothman, 1986; Koshy, 1990). Smaller arterioles and capillaries show distention, thrombosis, and vessel wall necrosis (Tuohy, 1997). Damaged, aberrant red blood cells (RBCs) adhere abnormally to the vascular endothelium and thereby trigger endothelial cell activation. Endothelial cell activation cascades into further disturbances, including a hypercoagulable state and abnormal vasomotor tone. The greater risk of stroke in young children with SCD may be explained by the higher cerebral blood flow velocity observed in this population (Powars, 2000).

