1500 mg ^a	1000 mg	500 mg

^a Voxelotor will be administered as 500 mg tablets.

Guidelines for dose reduction, hold, or permanent discontinuation of study drug for study drug-related AEs are provided in Table 6. If the AE resolves after a dose reduction, participants may resume study drug at the original dose, subject to the Investigator's discretion. The Medical Monitor may be consulted as needed regarding dose modifications.

^a Voxelotor will be administered as 500 mg tablets.

^a Voxelotor will be administered as 500 mg tablets.

Table 6: Dose Modification Guidelines for Study Drug-Related Adverse Events

Dose Reduction				
Event	Recommended Action			
Grade ≥ 2 (NCI grading scale) AE deemed considered related to study drug by the Investigator AND Precludes continued dosing at the current dose level due to safety concern or lack of tolerability (in the Investigator's judgment)	Study drug: May be reduced by one dose reduction. If, in the opinion of the Investigator, a Grade 2 AE has resolved to ≤ Grade 1, participant may resume study drug at the original dose. If, in the opinion of the Investigator, the AE poses a significant safety concern such that a dose hold is considered, the Investigator should contact the Medical Monitor.			
ALT ≥ 3 × ULN if ALT within normal limits at baseline OR > 3 × ULN AND a ≥ 2-fold increase above baseline value if elevated ALT value at baseline in the absence of additional signs of compromised liver function such as elevated PT, PTT, INR, elevated conjugated bilirubin, jaundice, or hepatic pain	Study drug: Confirm by repeat testing within 48 to 72 hours if possible, then repeat liver panel at least weekly until ALT level improves. Additional Actions: If ALT level continues to increase, reduce dose by one dose reduction and notify the Medical Monitor.			
ALT \geq 5 × and < 8 × ULN (confirmed by repeat testing within 48 to 72 hours) in the absence of additional signs of compromised liver function such as elevated PT, PTT, elevated conjugated bilirubin, jaundice, or hepatic pain	Study drug: Reduce dose by one dose reduction. Additional actions: Repeat liver panel test within 48 to 72 hours if possible and then at least weekly until resolution to < 5 × ULN; if ALT does not improve within 2 weeks of dose reduction, the Medical Monitor should be notified. If ALT continues to increase within 1 week after a dose reduction, dose should be interrupted, and the Medical Monitor should be notified.			

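### Appendix C excludes potential Hy's law cases that show hemolysis, in a hemolytic disease, and no planned table pairs transaminases with bilirubin

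*Protocol*

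**What the plan says.** **Disease.** Protocol 1.1 describes sickle cell disease as "marked by the pathophysiologic features of hemolytic anemia, vaso-occlusion, and progressive end-organ damage".

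**Definition.** Protocol Appendix C starts from normal AST/ALT and bilirubin. A potential Hy's law case then has AST/ALT of at least 3×ULN and total bilirubin of at least 2×ULN, "with no evidence of hemolysis and an alkaline phosphatase value" at or below 2×ULN or not available. Hemolysis is not defined.

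**Raised baseline.** Appendix C says that the threshold depends on the participant's "individual baseline values and underlying conditions". If AST, ALT or bilirubin is raised at baseline, "the following threshold values are used in the definition mentioned above, as needed, depending on which values are above the ULN at baseline". For bilirubin the rule reads: "Preexisting values of total bilirubin above the normal range: total bilirubin level increased from baseline value by an amount of" at least 1×ULN, or a value of at least 3×ULN, whichever is smaller.

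**SAE route.** Under 7.2.3 and Appendix C, potential Hy's law cases are reported as SAEs. The Appendix C sentence covers cases confirmed on repeat testing, "if no other reason for the LFT abnormalities has yet been found".

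**Analysis.** SAP 8.2.5 gives descriptive statistics, change and percent change from Day 1 for ALT, AST, alkaline phosphatase, total bilirubin, indirect bilirubin and LDH, each separately, plus participant listings. Direct bilirubin appears only in the formula for deriving a missing indirect value. There are no counts by multiple of the ULN and no display that pairs analytes.

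**The concern.** A condition that makes sense in a population without hemolysis is awkward here, because most of the population can be said to show evidence of hemolysis at any draw. A site that applies the definition word for word could decide that a participant with a new transaminase rise and raised bilirubin does not qualify. The Hy's law SAE report would then not be triggered.

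Safety is the study objective and SAEs are a named endpoint. If the site's attribution decides whether a case is reported, an independent check on the laboratory data is valuable. Summaries of ALT and of bilirubin taken separately cannot show whether the same participant had both raised.

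**Working it through.** The plan states no figure on this point, so the check is mainly a reading of the text.

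**1. Does the raised-baseline branch remove the hemolysis condition?** No. It supplies substitute thresholds for use inside the same definition, and only for AST/ALT and total bilirubin. For bilirubin at baseline B (in ×ULN, above 1) the trigger is min(B + 1, 3):

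| B | Trigger | Rise needed |
|---|---|---|
| 1.5 | min(2.5, 3) = 2.5 | 1.0 |
| 2.0 | min(3.0, 3) = 3.0 | 1.0 |
| 2.5 | min(3.5, 3) = 3.0 | 0.5 |
| 3.0 or more | 3.0 | none |

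The bilirubin part is therefore generous to participants with a high baseline. The exclusion comes from the hemolysis condition, which does not move with baseline.

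**2. What would count as evidence of hemolysis?** Protocol 1.4 names indirect bilirubin, reticulocytes and LDH as clinical measures of hemolysis. All three are collected under 6.10. Without a reference to the participant's own baseline, chronically abnormal values could satisfy the phrase.

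**3. Which other routes catch the case?**

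| Safeguard | What it does | What it leaves open |
|---|---|---|
| Appendix C SAE sentence | Refers to the AST/ALT and bilirubin criteria without repeating the hemolysis condition | Lapses if another reason has been found, and hemolysis can be offered as one |
| Appendix C work-up | Calls for direct and indirect bilirubin, GGT, PT/INR and albumin | Applies to cases already suspected |
| Sponsor review | Covers "any case where uncertainty remains as to whether it represents a potential" Hy's law case | A site confident in hemolysis has no uncertainty to refer; the clause sits in a sentence on rises weeks apart |
| Table 6, ALT above 3×ULN with raised conjugated bilirubin or jaundice | Dose hold and Medical Monitor contact, with no hemolysis condition | Keyed to ALT; no SAE requirement |
| Table 6, ALT at 3×ULN without other signs | Repeat test, "then repeat liver panel at least weekly until ALT level improves" | Same |
| 7.2.3 and SAP 8.2.2 | ALT rises needing follow-up are recorded and tabulated as AEs | Bilirubin pairing not shown |
| General SAE criteria (7.1.1) | Hospitalization and important medical events still qualify | Depends on judgment |
| DSMB (7.8) | Reviews safety data | Only for participants from GBT440-032 |

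Each reduces the risk. None removes the condition or guarantees a report by the Hy's law route.

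**4. Are the data for a paired table available?** Yes. Appendix A schedules serum chemistry, including ALT, AST, alkaline phosphatase, LDH and bilirubin fractions, at Day 1, Weeks 24 and 48, every 48 weeks and end of study. Hematology with reticulocytes falls at the same visits.

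**5. Why multiples of the ULN?** Testing is at local laboratories (6.10), and conversion to SI units does not remove differences in reference range. With assumed ULNs of 30 and 55 U/L, an ALT of 150 U/L is 150/30 = 5.0×ULN or 150/55 = 2.7×ULN.

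**6. What could a paired table say?** With zero cases among n participants, the one-sided 95% upper bound is 1 − 0.05^(1/n). For n = 600, the protocol's approximate maximum, it is 0.50%. For an assumed n = 300 it is 0.99%. This takes every participant as evaluable and ignores differences in follow-up.

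**The case against.** The strongest reply is that a true case is unlikely to slip through every route. The SAE sentence omits the hemolysis condition. The reason it asks for must explain the liver test abnormalities, and chronic hemolysis present at baseline does not obviously explain a new transaminase rise to 3×ULN. Reporting does not wait for etiology results. Table 6 acts on the individual in any event. This is a descriptive extension study, and a missing cross-table invalidates no planned result. These points stand, and they limit the finding to a wording risk and an absent check.

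Three stronger readings are tempting, and the documents do not support them:

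- **For a participant whose baseline bilirubin is at or above 3×ULN, only the hemolysis condition separates hepatic from hemolytic bilirubin.** The AST/ALT and alkaline phosphatase conditions still apply, and the work-up includes bilirubin fractions.
- **The report could not give a count of paired elevations.** Participant listings are planned, so the count could be extracted by hand. It is simply not tabulated in advance.
- **The condition should be replaced by a mandatory raised direct bilirubin.** That could lower sensitivity. A participant without hemolysis now qualifies on total bilirubin and would face a new hurdle. SAP 8.2.5 also allows for missing fractions.

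**Conclusion.** The concern holds as a gap worth fixing. The case definition contains an undefined condition that does not suit the population and survives the baseline adjustment, so a true case can miss the Hy's law SAE route. The SAP plans no table that would reveal it. A reader might infer that liver injury would go unreported or unseen; the partial safeguards and the listings do not bear that out.

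The number of cases affected cannot be derived, because the documents give no rate of liver injury or of baseline hyperbilirubinemia. The conclusion rests on a literal reading of Appendix C and on SAP 8.2.5 being the full list of planned laboratory outputs.

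**What to change.** **Protocol Appendix C**

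1. Remove background hemolysis as an exclusion. Any participant who meets the baseline-adjusted AST/ALT and total bilirubin thresholds, with alkaline phosphatase at or below 2×ULN or not available, is evaluated and reviewed with the sponsor.
2. State that hemolysis counts as another reason only if it has worsened beyond the participant's own baseline and also explains the transaminase rise.
3. Treat raised direct bilirubin as supporting evidence, not as a required criterion.
4. Minor wording: the statement that liver tests are not routine conflicts with the serum chemistry scheduled in Appendix A and, at PK sites, Appendix B. Say that the appendix applies to scheduled and unscheduled results.

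**SAP 8.2.5**

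1. Add direct bilirubin to the summaries.
2. Express ALT, AST, alkaline phosphatase and bilirubin as multiples of the local ULN.
3. Count participants whose worst post-Day-1 ALT or AST is at least 3×, 5× and 8×ULN.
4. Cross-tabulate these against concurrent total bilirubin (at least 2×ULN, and the baseline-adjusted trigger) and direct bilirubin, with the meaning of concurrent stated.
5. List these participants with same-draw bilirubin fractions, alkaline phosphatase and LDH, and same-visit reticulocytes, regardless of hemolysis attribution.

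**Cost.** A few tables and one listing, plus wording at the next amendment; no new visits or samples. Some extra cases will need review, and some will prove hemolytic, particularly where baseline bilirubin already meets the trigger. If local ULNs are not in the database, they must be entered for up to about 70 sites, by age where ranges differ. Protocol 10.3 already has sites supply reference ranges as appropriate.
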